10.10.5. Safety Tables

Safety: Tables					
No.	Population	GSK Standard/ Example Shell	Title	Programming Notes	Deliverable [Priority]
Adverse Events (AEs)					
2.1.	Safety	AE1	Summary of Adverse Events by System Organ Class and Preferred Term– Part 1 & Part 2	Include pooled treatment groups by dose & route	Cohort 1-5, EOS
2.2.	Safety – Injection Exposed	ISR1	Subject-Level Summary of Injection Site Reaction Adverse Events by Period and Preferred Term – Part 1 & Part 2	Injection 1 and Injection 2 periods only.	Cohort 1-5 IA Cohort 1-4, Cohort 1-5, EOS
2.3.	Safety – Injection Exposed	ISR1a	Subject-Level Summary of Maximum Impact on Usual Social and Functional Activities across all Grade ≥ 2 Injection Site Reaction Adverse Events of Erythema/Redness and/or Induration/Swelling by Period – Part 1 & Part 2 (Cohorts 2, 4, 4b and 5)	Injection 1 and Injection 2 periods only. Include pooled treatment groups by dose & route	Cohort 1-5 IA Cohort 1-4, Cohort 1-5, EOS
2.4.	Safety – Injection Exposed	ISR2	Event-level Summary of Injection Site Reaction Adverse Events by Preferred Term – Part 1 & Part 2	Injection 1 and Injection 2 periods only. Include pooled treatment groups by dose & route	Cohort 1-5 IA Cohort 1-4, Cohort 1-5, EOS

Safety: Tables					
No.	Population	GSK Standard/ Example Shell	Title	Programming Notes	Deliverable [Priority]
2.5.	Safety – LA Exposed	ISR2a	Summary of Injection Site Reaction Adverse Events by Preferred Term – Impact on Social & Function Activities, and Occurrence of Other Associated Grade 3 ISRs or Potentially Life-Threatening Consequences – Part 1 Cohort 4h	Injection 1 and Injection 2 periods only. Include pooled treatment groups by dose & route.	Cohort 1-5 IA Cohort 1-4, Cohort 1-5, EOS
2.6.	Safety	AE1	Summary of Drug-Related Adverse Events by System Organ Class and Preferred Term – Part 1 & Part 2	Include pooled treatment groups by dose & route	Cohort 1-5, EOS
2.7.	Safety	AE15	Summary of Common ($\geq 5\%$) Non-serious Adverse Events by System Organ Class and Preferred Term – Part 1 & Part 2 (Number of Subjects and Occurrences)	Include pooled treatment groups by dose & route	Cohort 1-5, EOS
2.8.	Safety	AE16	Summary of Serious Adverse Events by System Organ Class and Preferred Term – Part 1 & Part 2 (Number of Subjects and Occurrences)	Include pooled treatment groups by dose & route	Cohort 1-5, EOS
2.9.	Safety	AE5B	Summary of Adverse Events by System Organ Class and Preferred Term and Maximum Grade – Part 1 & Part 2	Include pooled treatment groups by dose & route	Cohort 1-5 IA Cohort 1-4, Cohort 1-5, EOS
2.10.	Safety	AE5B	Summary of Drug-Related Adverse Events by System Organ Class and Preferred Term and Maximum Grade – Part 1 & Part 2	Include pooled treatment groups by dose & route	Cohort 1-5 IA Cohort 1-4, Cohort 1-5, EOS
2.11.	Safety	ESI1	Summary of Characteristics of Seizures		Cohort 1-5, EOS
COVID-19 Assessment					
2.12.	Safety	PAN1	Summary of COVID-19 Assessments for Subjects with COVID-19 Adverse Events – Part 1 & Part 2		Cohort 1-5, EOS
2.13.	Safety	PAN2	Summary of COVID-19 Additional Assessments for Subjects with COVID-19 Adverse Events – Part 1 & Part 2		Cohort 1-5, EOS
2.14.	Safety	PAN3	Summary of COVID-19 Symptoms for Subjects with COVID-19 Adverse Events – Part 1 & Part 2		Cohort 1-5, EOS

CONFIDENTIAL

212482

Safety: Tables					
No.	Population	GSK Standard/ Example Shell	Title	Programming Notes	Deliverable [Priority]
2.15.	Safety	PAN4	Summary of COVID-19 Pandemic Visit Impacts – Part 1 & Part 2		Cohort 1-5, EOS
Laboratory: Chemistry					
2.16.	Safety	LB1	Summary of Clinical Chemistry Values – Part 1 & Part 2		Cohort 1-5, EOS
2.17.	Safety	LB1	Summary of Clinical Chemistry Changes from Baseline – Part 1 & Part 2		Cohort 1-5, EOS
2.18.	Safety	LB16A	Summary of Clinical Chemistry Results by Maximum Grade Increase Post-Baseline Relative to Baseline – Part 1 & Part 2	Unscheduled visits are included for determining maximum grade	Cohort 1-5 IA Cohort 1-4, Cohort 1-5, EOS
Laboratory: Hematology					
2.19.	Safety	LB1	Summary of Hematology Values – Part 1 & Part 2		Cohort 1-5, EOS
2.20.	Safety	LB1	Summary of Hematology Changes from Baseline – Part 1 & Part 2		Cohort 1-5, EOS
2.21.	Safety	LB16A	Summary of Hematology Results by Maximum Grade Increase Post-Baseline Relative to Baseline – Part 1 & Part 2	Unscheduled visits are included for determining maximum grade	Cohort 1-5 IA Cohort 1-4, Cohort 1-5, EOS
Laboratory: Coagulation					
2.22.	Safety	LB1	Summary of Coagulation Values – Part 1 & Part 2		Cohort 1-5, EOS
2.23.	Safety	LB1	Summary of Coagulation Changes from Baseline – Part 1 & Part 2		Cohort 1-5, EOS
2.24.	Safety	LB16A	Summary of Coagulation Results by Maximum Grade Increase Post-Baseline Relative to Baseline – Part 1 & Part 2	Unscheduled visits are included for determining maximum grade	Cohort 1-5, EOS
ECG					

Safety: Tables					
No.	Population	GSK Standard/ Example Shell	Title	Programming Notes	Deliverable [Priority]
2.25.	Safety	SAFE_T1 (See EG1)	Summary of ECG Findings – Part 1 & Part 2–	Unscheduled visits are included for determining worst-case post-baseline	Cohort 1-5, EOS
2.26.	Safety	EG2	Summary of ECG Values – Part 1 & Part 2		Cohort 1-5, EOS
2.27.	Safety	EG2	Summary of ECG Changes from Baseline – Part 1 & Part 2		Cohort 1-5, EOS
2.28.	Safety	SAFE_T2 (See EG10A)	Summary of Maximum QTc Values Post-Baseline Relative to Baseline by Category – Part 1 & Part 2	Unscheduled visits are included for determining maximum QTc values	Cohort 1-5 IA Cohort 1-4, Cohort 1-5, EOS
2.29.	Safety	SAFE_T3 (See EG11)	Summary of Maximum Increase in QTc Values Post-Baseline Relative to Baseline by Category – Part 1 & Part 2	Unscheduled visits are included for determining maximum increase in QTc values	Cohort 1-5 IA Cohort 1-4, Cohort 1-5, EOS
Vital Signs					
2.30.	Safety	VS1	Summary of Vital Sign Values - Part 1 & Part 2		
2.31.	Safety	VS1	Summary of Vital Sign Changes from Baseline – Part 1 & Part 2		Cohort 1-5, EOS
2.32.	Safety	SAFE_T4 (See VS3)	Summary of Vital Sign Results Relative to Potential Clinical Importance (PCI) Criteria Post-Baseline Relative to Baseline – Part 1 & Part 2	Unscheduled visits are included for determination of 'to Low' and 'to High'	Cohort 1-5 IA Cohort 1-4, Cohort 1-5, EOS
Liver Events					
2.33.	Safety	LIVER1	Summary of Liver Stopping Event Reporting – Part 1 & Part 2		Cohort 1-5 IA Cohort 1-4, Cohort 1-5, EOS

Safety: Tables					
No.	Population	GSK Standard/ Example Shell	Title	Programming Notes	Deliverable [Priority]
2.34.	Safety	LIVER10	Summary of Hepatobiliary Laboratory Abnormalities – Part 1 & Part 2	Unscheduled visits are included	Cohort 1-5, EOS
Questionnaires					
2.35.	Safety	SAFE_T5	Summary of Numeric Rating Scale – Part 1 & Part 2	For each period: by visit, maximum and AUC. AUC not needed for Cohort 1-5 IA	Cohort 1-5 IA Cohort 1-4, Cohort 1-5, EOS
2.36.	Safety	SAFE_T6	Summary of Perception of Injection – Part 1 & Part 2		Cohort 1-5 IA Cohort 1-4, Cohort 1-5, EOS
Injection Site Area & Duration by Grade					
2.37.	Safety	SAFE_T7a	Event-Level Summary of Duration (Days) at Each Grade by Injection Site Reaction Preferred Term – Part 1 & Part 2	Injection 1 and Injection 2 periods only. Include pooled treatment groups by dose & route	Cohort 1-5 IA Cohort 1-4, Cohort 1-5, EOS

Safety: Tables					
No.	Population	GSK Standard/ Example Shell	Title	Programming Notes	Deliverable [Priority]
2.38.	Safety	SAFE_T7b	Event-Level Summary of Duration (Days) at Each Grade – Grading determined according to DAIDS Impact on Social and Function Activities Categories and Occurrence of Other Associated Grade 3 ISRs or Potentially Life-Threatening Consequences – Part 1 Cohort 4h	Repeat for each of the following grouped preferred terms: Erythema/Redness/Induration/Swelling, Erythema/Redness, and Induration/Swelling Injection 1 and Injection 2 periods only. Include pooled treatment groups by dose & route	Cohort 1-5 IA Cohort 1-4, Cohort 1-5, EOS
2.39.	Safety	SAFE_T7c	Subject-Level Summary of Maximum Duration (Days) at Each Grade by Injection Site Reaction Preferred Term – Part 1 & Part 2	Injection 1 and Injection 2 periods only. Include pooled treatment groups by dose & route	Cohort 1-5 IA Cohort 1-4, Cohort 1-5, EOS
2.40.	Safety	SAFE_T7d	Subject-Level Summary of Maximum Duration (Days) at Each Grade – Grading determined according to DAIDS Impact on Social and Function Activities Categories and Occurrence of Other Associated Grade 3 ISRs or Potentially Life-Threatening Consequences – Part 1 Cohort 4h	Repeat for each of the following grouped preferred terms: Erythema/Redness/Induration/Swelling, Erythema/Redness, and Induration/Swelling Injection 1 and Injection 2 periods only. Include pooled treatment groups by dose & route	Cohort 1-5 IA Cohort 1-4, Cohort 1-5, EOS

Safety: Tables					
No.	Population	GSK Standard/ Example Shell	Title	Programming Notes	Deliverable [Priority]
2.41.	Safety	SAFE_T8	Subject- CCI 

 

 

	Injection 1 and Injection 2 periods only.	Cohort 1-4, Cohort 1-5, EOS
Crossover Statistical Analyses for Cohort 4b, including summaries of endpoints for other cohorts					
2.42.	Safety – LA Exposed (Complete Case)	SAFE_XO1	Statistical Analysis for Proportion of Participants with Injection Site Reactions – CCI 

 

 

	CCI 

	Cohort 1-5, EOS
2.43.	Safety – LA Exposed (Complete Case)	SAFE_XO2	CCI 

		Cohort 1-5, EOS
2.44.	Safety – LA Exposed (Complete Case)	SAFE_XO3			Cohort 1-5, EOS
2.45.	Safety – LA Exposed (Complete Case)	PIN_XO1			Cohort 1-5, EOS
2.46.	Safety – LA Exposed (Complete Case)	PIN_XO2			Cohort 1-5, EOS

Safety: Tables					
No.	Population	GSK Standard/ Example Shell	Title	Programming Notes	Deliverable [Priority]
2.47.	Safety – LA Exposed (Complete Case)	NRS_XO1	CCI		Cohort 1-5, EOS
2.48.	Safety – LA Exposed (Complete Case)	PRF_XO1			Cohort 1-5, EOS

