Section 8.1.5.1 Statistical Methodology Specification	• Clarified plan to perform PK pairwise comparisons between cohorts receiving the same dose. • Updated dose proportionality assessment to be performed separately for each route rather than across routes.
Section 2.2 Study Objectives and Estimands	• Exploratory endpoint CCI [REDACTED] [REDACTED]
Section 10.2 Appendix 2: Schedule of Activities	• Update protocol defined schedule of events per protocol amendment 6.
Section 10.3: Assessment Windows	• Clarified that all assessments/events, including PK, will be assigned to assessment windows/analysis visits. • Analysis windows were updated to incorporate cohort 4b and 4h assessments and other minor corrections.

Section 10.4: Appendix 4: Study Phases, Study Periods, and Treatment Emergent Adverse Events	
 Added analysis period derivation details for CCI [REDACTED]
Section 10.6.3 Safety	
 CCI [REDACTED] CCI [REDACTED]
Section 10.10 Appendix 10: List of Data Displays	
 CCI [REDACTED] Added displays to summarize clinical chemistry, hematology, coagulation, ECG and vitals sign values (in addition to change from baseline) Updated analysis population to Safety – LA Exposure for ISR displays Updated delivery classifications (i.e., Cohort 1-5 IA, Cohort 1-5, EOS). Combined separate Part 1 and Part 2 displays into a single display. Additional programming notes added Updated presentation of treatment groups in the table shells document.
General	
 Minor editorial and document formatting revisions

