The requirement for an optional further cohort (Cohort 6) will be based upon a review of the available safety, tolerability, and PK data from Cohorts 1-4 and safety, tolerability and PK data (12 weeks after injection 1) from Cohort 5 and comparison to historical PK data of the CAB 200 mg/mL formulation from the Phase 2/3 program. This determination will be undertaken by the STR. Cohort 6, if required, will assess the PK, safety and tolerability of alternative doses and/or dosing schedule among 22 participants (20 active and 2 active control). Sentinel dosing will also occur for this cohort.

At a 05 October 2021 STR meeting, it was agreed

- to stop the injection immediately in Cohort 5. As a consequent, all participants enrolled in Cohort 5 would not receive Injection 2
- that Cohort 6 was not needed

Analyses described in this RAP are adjusted accordingly

Dosing	
 • See Study Design Schematics above and Protocol Amendment 06 Section 6.1.2.
---------------	--

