5. CONSIDERATIONS FOR DATA ANALYSES AND DATA HANDLING CONVENTIONS

5.1. Study Treatment & Sub-group Display Descriptors

In general, the following treatment group descriptors will be presented in data displays for reporting, with minor variations depending on whether a display is presenting treatment group information as a column or row.

For Cohort 4b, all data will be summarized by period (OLI, injection 1, injection 2, follow-up, overall) and selected safety and patient reported outcome endpoints will also be summarized by CCI PK concentrations and parameters will also be summarized by treatment sequence and period, as appropriate.

Treatment Group Descriptions					
		Randomization		Data Displays for Reporting	
Part	Arm	Code	Description	Description	Order in TLF
Part 1	C1 CAB 400	A1	CAB 400 mg/mL IM injections 4-weeks apart in gluteus muscle (cohort 1)	Oral CAB 30 mg QD	1
				Inj.1 600 mg IM Gluteal	2
				Inj.2 400 mg IM Gluteal	3
				Follow-up	4
				Overall ¹	5
	C1 CAB 200	C1	CAB 200 mg/mL IM Injection 4-weeks apart in gluteus muscle (cohort 1)	Oral CAB 30 mg QD	6
				Inj.1 600 mg IM Gluteal	7
				Inj.2 400 mg IM Gluteal	8
				Follow-up	9
				Overall ¹	10
	C2 CAB 400	A2	CAB 400 mg/mL SC injections 4-weeks apart in abdomen (cohort 2)	Oral CAB 30 mg QD	11
				Inj.1 600 mg SC Abdomen	12
				Inj.2 200 mg SC Abdomen	13
				Follow-up	14
				Overall ¹	15
	C2 CAB 200	C2	CAB 200 mg/mL SC injections 4-weeks apart in abdomen (cohort 2)	Oral CAB 30 mg QD	16
				Inj.1 300 mg SC Abdomen	17
				Inj.2 100 mg SC Abdomen	18
				Follow-up	19
				Overall ¹	20
	C3 CAB 400	A3	CAB 400 mg/mL IM injections 4-weeks apart in	Oral CAB 30 mg QD	21
				Inj. 1 600 mg IM Lateral Thigh	22
				Inj. 1 400 mg IM Lateral Thigh	23

			lateral thigh (cohort 3)	Inj. 2 400 mg IM Lateral Thigh	24
				Follow-up	25
				Overall ¹	26
	C3 CAB 200	C3	CAB 200 mg/mL IM injections 4- weeks apart in lateral thigh (cohort 3)	Oral CAB 30 mg QD	27
				Inj.1 600 mg IM Lateral Thigh	28
				Inj.1 400 mg IM Lateral Thigh	29
				Inj.2 400 mg IM Lateral Thigh	30
				Follow-up	31
				Overall ¹	32
	C4 CAB 400	A4	CAB 400 mg/mL Injections 4-weeks apart (first IM injection in gluteus medius and second SC injection in abdomen; cohort 4)	Oral CAB 30 mg QD	33
				Inj.1 400 mg IM Gluteal	34
				Inj.2 200 mg SC Abdomen	35
				Follow-up	36
				Overall ¹	37
	C4 CAB 200	C4	CAB 200 mg/mL Injections 4-weeks apart (first IM injection in gluteus medius and second SC injection in abdomen; cohort 4)	Oral CAB 30 mg	38

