				Inj.1 400 mg IM Gluteal	39
				Inj.2 100 mg SC Abdomen	40
				Follow-up	41
				Overall ¹	42
	C4b CAB 400 + Topical Steroid or NSAID 4	A4bG1	CAB 400 mg/mL Injections 4- weeks apart in CCI	Oral CAB 30 mg QD	43
				CCI	44
				CCI	45
				Follow-up	46
				Overall ¹	47
	C4b CAB 400 + Topical Steroid or NSAID 4	A4bG2	CAB 400 mg/mL Injections 4- weeks apart in CCI	Oral CAB 30 mg QD	4833
				CCI	49
				CCI	50
				Follow-up	51
				Overall ¹	52
		A4h		Oral CAB 30 mg QD	53

	C4h CAB 400 + rHUPH20		CAB 400 mg/mL Injection in the abdomen with rHuPH20	Inj. 1 CAB 400 mg + 5000 U rHUPH20 SC Abdomen	54
				Follow-up	55
				Overall ¹	56
	C4h CAB 200 + rHUPH20	A4h	CAB 200 mg/mL Injection in the abdomen with rHuPH20	Oral CAB 30 mg QD	57
				Inj. 1 CAB 400 mg + 5000 U rHUPH20 SC Abdomen	58
				Follow-up	59
				Overall ¹	60
	N/A	N/A	Pooled Group ²	Pooled Oral CAB 30 mg QD OLI ONLY	61
				Pooled Oral CAB 30 mg QD	62
				Pooled CAB 400 mg/mL Q4W 400 mg IM Gluteal	63
				Pooled CAB 200 mg/mL Q4W 400 mg IM Gluteal	64
				Pooled CAB 400 mg/mL Q4W 200 mg SC	65
				Pooled CAB 200 mg/mL Q4W 100 mg SC	66
				Pooled CAB 400 mg/mL Q4W 400 mg Lateral Thigh	67
				Pooled CAB 200 mg/mL Q4W 400 mg Lateral Thigh	68
Part 2	C5 CAB 400 ³	A5	CAB 400 mg/mL IM injections 12-weeks apart in gluteus muscle (cohort 5)	Oral CAB 30 mg QD	69
				Inj. 1 800 mg IM Gluteal	70
				Follow-up	71
				Overall ¹	72
	C5 CAB 200	C5	CAB 200 mg/mL IM injections 12-weeks apart in gluteus muscle (cohort 5)	Oral CAB 30 mg QD	73
				Inj. 1 400 mg IM Gluteal	74
				Follow-up	75
				Overall ¹	76
	N/A	N/A	Historical Data, CAB 200 mg/mL	(ATLAS/FLAIR) Inj. 1 CAB 600 mg IM Gluteal ³	77
				(ATLAS/FLAIR) Inj. 2 CAB 400 mg IM Gluteal ³	78
				(ÉCLAIR) Inj. 1 CAB 800 mg IM Gluteal ³	79

Note: A1 = Active Drug in Cohort 1; A2 = Active Drug in Cohort 2; A3 = Active Drug in Cohort 3; A4 = Active Drug in Cohort 4; A4h = Active Drug in Cohort 4h; A5 = Active Drug in Cohort 5; A6 = Active Drug in Cohort 6; C1 = Cohort 1, C2 = Cohort 2, C3 = Cohort 3, C4 = Cohort 4, C4b = Cohort 4b, C4h = Cohort 4h, C5 = Cohort 5.

1. Overall group is not applicable for PK analyses.
2. Pooled active and AC groups are only applicable when there is more than one cohort at the stated dose (mg) to combine for the specific summary.
3. Historical data for formulation of 200 mg/mL from the Phase 3 program, only applicable for PK analyses.

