10.4. Appendix 4: Study Phases, Study Periods, and Treatment Emergent Adverse Events

10.4.1. Study Phases and Study Periods

All assessments and events (including those collected as planned, early withdrawal and unscheduled visits) will be classified in study phases and study periods according to [Table 4](#) and [Table 5](#), respectively.

Assessments/events are assigned to study phases, and study periods sequentially, starting from the top of each table.

Table 4 Assignment of Study Phases

Study Phase	Definition
Screen	Assessments/Events assigned to Period=Screen in Table 5
OLI	Assessments/Events assigned to Period=OLI in Table 5
Injection	Assessments/Events assigned to Period=Injection 1 or Period=Injection 2 in Table 5
Follow-up	Assessments/Events assigned to Period=Follow-up in Table 5

Table 5 Assignment of Study Periods

For Adverse Events	
Study Period	Date range
Screen	If actual “Time of Day” for the assessment/event is collected:
	AE Start Date and Time < OLI Treatment Start Date & Time
	If actual “Time of Day” for the assessment/event is not collected:
	AE Start Date < OLI Treatment Start Date
OLI	If actual “Time of Day” for the assessment/event is collected:
	For participants continuing into Injection Phase: OLI Treatment Start Date & Time ≤ AE Start Date & Time < Date & Time of First CAB Injection
	For participants not continuing into Injection Phase: AE Start Date & Time ≥ OLI Treatment Start Date & Time
	If actual “Time of Day” for the assessment/event is not collected:
	For participants continuing into Injection Phase: OLI Treatment Start Date ≤ AE Start Date < Date of First CAB Injection
	For participants not continuing into Injection Phase: AE Start Date ≥ OLI Treatment Start Date
Injection 1	If actual “Time of Day” for the assessment/event is collected:
	For participants receiving second CAB injection: Date & Time of First CAB Injection ≤ AE Start Date & Time < Date & Time of Second CAB Injection
	For participants not receiving second CAB injection: Date & Time of First CAB Injection ≤ AE Start Date & Time and AE Start Date ≤ Date of Nominal Follow-up Week 4/Day 28 Visit [for Part 1 participants]/ Nominal Follow-up Week 12 Visit [for Part 2 participants]

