	If actual “Time of Day” for the assessment/event is not collected: For participants receiving second CAB injection: Date of First CAB Injection ≤ AE Start Date < Date of Second CAB Injection For participants not receiving second CAB injection: Date of First CAB Injection ≤ AE Start Date ≤ Date of Nominal Follow-up Week 4/Day 28 Visit [for Part 1 participants]/ Nominal Follow-up Week 12 Visit [for Part 2 participants]
Injection 2	If actual “Time of Day” for the assessment/event is collected: Date & Time of Second CAB Injection ≤ AE Start Date & Time and AE Start Date ≤ Date of Nominal Follow-up Week 4/Day 28 Visit [for Part 1 participants]/ Nominal Follow-up Week 12 Visit [for Part 2 participants] If actual “Time of Day” for the assessment/event is not collected: Date of Second CAB Injection ≤ AE Start Date ≤ Date of Nominal Follow-up Week 4/Day 28 Visit [for Part 1 participants]/ Nominal Follow-up Week 12 Visit [for Part 2 participants]
Follow-up	AE Start Date > Date of Nominal Follow-up Week 4/Day 28 Visit [for Part 1 participants]/ Nominal Follow-up Week 12 Visit [for Part 2 participants]
For Injection Site Reaction Adverse Events (Where collected on the ISR form for study treatment associated reactions, including drug related and non-drug related)	
Injection 1	If actual “Time of Day” for the assessment/event is collected: For participants receiving second CAB injection: Date & Time of First CAB Injection ≤ AE Start Date & Time < Date & Time of Second CAB Injection For participants not receiving second CAB injection: Date & Time of First CAB Injection ≤ AE Start Date & Time If actual “Time of Day” for the assessment/event is not collected: For participants receiving second CAB injection: Date of First CAB Injection ≤ AE Start Date < Date of Second CAB Injection For participants not receiving second CAB injection: Date of First CAB Injection ≤ AE Start Date

Injection 2	If actual "Time of Day" for the assessment/event is collected:
	Date & Time of Second CAB Injection ≤ AE Start Date & Time and AE Start Date
	If actual "Time of Day" for the assessment/event is not collected:
	Date of Second CAB Injection ≤ AE Start Date
For PK Data	
Study Period	Data Range
OLI	Excluding Injection 1 Day 1 Pre-dose Samples: Start Date & Time < Date & Time of First CAB Injection

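### In the merged safety tables the Injection 1 column covers about 84 days for Cohort 5 and about 28 days for Part 1, with 10 versus 3 chemistry and haematology windows, so crude percentages and worst grades are not comparable there.

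*SAP*

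**What the plan says.** The RAP amendment (SAP 1.1) records the change: "Combined separate Part 1 and Part 2 displays into a single display". SAP 5.1 sets the columns: "In general, the following treatment group descriptors will be presented in data displays for reporting", and the list runs by arm and then by period (oral, Injection 1, Injection 2, follow-up, overall). Cohort 5's injection column is "Inj. 1 800 mg IM Gluteal"; the largest Part 1 Injection 1 dose is 600 mg.

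SAP 10.4.1, Table 5, defines the periods. For a participant who has a second injection, the Injection 1 adverse event period is "Date & Time of First CAB Injection ≤ AE Start Date & Time < Date & Time of Second CAB Injection". In Part 1 the second injection is due at Week 4 ± 3 days. A participant without a second injection is followed in this period to the nominal Week 4 visit in Part 1 and, in Part 2, to the "Nominal Follow-up Week 12 Visit [for Part 2 participants". SAP 2.3 records the decision that "all participants enrolled in Cohort 5 would not receive Injection 2", so the Week 12 visit closes the period for Cohort 5.

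The tables affected are adverse event Tables 2.1 ("Summary of Adverse Events by System Organ Class and Preferred Term"), 2.6, 2.7, 2.9 and 2.10; laboratory Tables 2.18 ("Summary of Clinical Chemistry Results by Maximum Grade Increase Post-Baseline Relative to Baseline") and 2.21 (the same for haematology); and hepatobiliary Table 2.34. SAP 10.6.1 lets measurements outside the by-visit summaries count toward the worst case, and the notes to these laboratory tables bring in unscheduled visits. The list of displays includes an exposure summary (Table 1.10), but no exposure-adjusted event rate, common four-week cut or matched-visit worst grade.

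**The concern.** A cumulative percentage grows with the time observed, and a worst value grows with the number of values from which it is taken. Both differ here between columns that stand side by side, and the difference is tied to dose: the arm with the longest and densest Injection 1 observation is also the one with the highest dose. A reader comparing 800 mg with 400 or 600 mg in these columns cannot separate dose from observation.

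Safety and tolerability is a stated objective, and liver biochemistry abnormalities are a secondary endpoint. Tables 2.9, 2.10, 2.18 and 2.21 are also listed for the Cohort 1-5 interim analysis, whose purpose is to disseminate results. For adverse events the mismatch is mainly one of length, because the visits up to Day 22 are almost the same. For laboratory grades it is both length and density.

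**Working it through.** **Period length.** Part 1, from first to second injection (or to the nominal Week 4 visit): about 28 days. Cohort 5, from the injection to the nominal Week 12 visit: about 84 days. Ratio 84/28 = 3.

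**Chemistry and haematology windows after Injection 1** (SAP 10.3.1, Tables 2 and 3):
- Part 1: Day 8 (days 2-11), Day 14 (days 12-21), Week 4 (day 22 onward) = 3. For two-injection cohorts the Week 4 value is the Injection 2 Day 1 sample, which Table 5 assigns to Injection 1.
- Cohort 5: Days 2, 3, 5, 7, 10, 14 and 22 and Weeks 4, 8 and 12 = 10. Eight of these fall at or before Week 4.
- Cohort 4h: the schedule adds draws on Days 3 and 5, so 5 scheduled draws, all eligible for the worst grade.

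**If worst grade is tabulated per Injection phase instead of per period.** Two-injection Part 1 cohorts have 3 + 3 = 6 windows over about 8 weeks, against 10 over about 12 weeks for Cohort 5.

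**Overall columns.** Time after the first injection is 4 + 52 = 56 weeks for two-injection Part 1 cohorts, and 52 weeks for Cohorts 4h and 5. Laboratory times are 6 + 5 = 11, 5 + 5 = 10 and 10 + 3 = 13 respectively.

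**Illustration for adverse events.** The documents give no event rates, so p, the 28-day risk, is assumed. With a constant hazard the 84-day risk is 1 − (1 − p)³:
- p = 10%: 1 − 0.9³ = 27.1%
- p = 20%: 1 − 0.8³ = 48.8%
- p = 30%: 1 − 0.7³ = 65.7%

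With the planned active numbers and p = 10%, this is 20 × 0.271 = 5.4 participants expected in Cohort 5 against 18 × 0.10 = 1.8 in a Part 1 cohort. If every event falls in the first four weeks, the 84-day risk equals p and there is no inflation.

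**Illustration for worst grade.** The per-draw chance q of a grade increase is also assumed, with independent draws. The chance of at least one in k draws is 1 − (1 − q)^k:

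| q | k = 3 | k = 5 | k = 6 | k = 8 | k = 10 |
|---|---|---|---|---|---|
| 2% | 5.9% | 9.6% | 11.4% | 14.9% | 18.3% |
| 5% | 14.3% | 22.6% | 26.5% | 33.7% | 40.1% |

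The k = 8 column shows that cutting Cohort 5 at Week 4 would equalise length but leave most of the laboratory excess.

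**The case against.** Several points on the other side stand.

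- **Tabulation unit.** No programming note for Tables 2.18, 2.21 or 2.34 says that worst grade is taken per injection period. SAP 5.2 defines baselines per phase, the column list in SAP 5.1 applies only in general, and the table shells are in a separate document. A reader might infer that 10 versus 3 is certain for the worst-grade tables; the documents also allow about 10 versus 6. That is still unequal, and the Part 1 side would then include a second injection.
- **Other displays.** The Overall columns are roughly balanced, and the Follow-up columns cover a longer span in Part 1 (Weeks 4-52 against 12-52). By-visit laboratory tables allow comparison at shared visits, but they show values and changes, not a worst grade. Cohort 5's own CAB 200 mg/mL controls share its window, but there are only two.
- **Purpose.** The safety objectives name injection sites, not dose, and no hypothesis is tested. Descriptive columns placed side by side are still read as a comparison.
- **Extra monitoring is deliberate.** The additional Part 2 draws were added to watch higher doses more closely. A matched column that replaced the full result could miss a true early or late elevation. This limits what the remedy may do; it does not make the columns comparable.
- **Size.** Repeat draws in one person are correlated, so the independent-draw figures are an upper range, and the hazard may not be constant.

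The tempting stronger reading is that Cohort 5 will look less safe and that any excess will be an artefact. The documents do not support it: they give neither the rate nor the timing of events, and a real dose effect could be present as well.

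**Conclusion.** The point holds for the Injection 1 columns of Tables 2.1, 2.6, 2.7, 2.9, 2.10, 2.18, 2.21 and 2.34. Observation there is about three times as long for the 800 mg group, with 10 versus 3 chemistry and haematology windows (5 scheduled draws in Cohort 4h; about 10 versus 6 for two-injection cohorts if tabulated per phase). These counts come from the SAP itself. That Cohort 5 can show higher crude percentages and worst grades at an equal rate follows from them; by how much does not. The effect on adverse events is nil if they all occur early, and about 2.2-fold to 2.7-fold (65.7/30 to 27.1/10) for 28-day risks of 30% down to 10% under a constant hazard. The laboratory range of 6-14% against 18-40% rests on the assumed 2-5% per draw and on independence.

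The point does not extend to the Overall columns, and coagulation Table 2.24 is not part of the 10-versus-3 contrast. It is a cheap improvement, not an error that invalidates an analysis.

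**What to change.** 1. **Adverse events other than injection site reactions** (Tables 2.1, 2.6, 2.7, 2.9, 2.10): add a Cohort 5 column headed Injection 1, first 28 days, counting events with onset by Day 28 after Injection 1. Use it for any comparison with the Part 1 Injection 1 columns.
2. **Tables 2.18, 2.21 and 2.34:** add a supplementary matched-visit worst-grade column in all cohorts, built only from the scheduled draws at nominal Day 7 (Cohort 5) or Day 8 (Part 1), Day 14 and Week 4, one draw per visit. Select by nominal visit, not by the existing windows: Cohort 5 has no Day 8 laboratory window (its nearest is Day 7, days 7-8), Part 1's Day 8 window would admit five Cohort 5 draws (Days 2, 3, 5, 7 and 10), and the Part 2 Week 4 window (days 26-42) runs past Day 28.
3. **Keep the full-interval columns**, using every measurement, as the main safety result, so that no early or late finding at the highest dose is dropped.
4. **Footnote** the period length and the number of draws for each column, and state whether worst grade is per period or per phase.

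The cost is extra programming and columns, with no new data. The downside is that the matched laboratory column is less sensitive than the full one, which is why it should only supplement it.
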